### Run-in period

The study will start with a 12-week run-in period. Subjects will have either been treated or untreated with a PPI prior to entering this phase of the study. The subjects will receive both oral and written subject information and sign a consent form. At visit 1 all subjects will undergo a physical examination, including vital signs and demographics. Medical and surgical history, especially for GERD will be recorded.

All subjects will attend an "Investigational week". This "week" will allow the collection of baseline data, such as endoscopy with biopsy sampling, 24-hour pH metry, manometry, SAP and laboratory measurements. A 24-hour pH metry performed within 12 months prior to enrolment could be accepted, if made according to the method stated i.e. no antisecretory medication 7 days prior to investigation. Manometry will only be performed at the first occasion of pH metry in all subjects.

The "investigational week" can take place either immediately or 6 weeks after treatment with esomeprazole 40 mg o.d. depending on:

- Whether the subject was treated or untreated with PPI prior to enrolment
- Whether the clinic can offer 24 hr pH metry and SAP within 2 weeks from visit 1 for the untreated subjects.

Esomeprazole must be withheld at least 7 days (visit 2) prior to the "Investigational week".

Dose adjustments are not allowed during the run-in period.

### **Subjects treated with PPI prior to study start will be treated in one of two ways depending on:**

- (i) if the subject is known (endoscopically) to the investigator prior to entry into the study. These subjects need not undergo an endoscopy at visit 1, but will receive esomeprazole 40 mg o.d. and continue with visit 2 and 3 as scheduled.
- (ii) if the subject is referred to endoscopy, the subject will undergo endoscopy at visit 1 and receive esomeprazole 40 mg o.d. and continue with visit 2 and 3 as scheduled.

The “Investigational week” will take place during visit 3. In case of mucosal breaks classified as LA grade C or D at visit 3 a new endoscopy must be done at visit 4 prior to randomization to exclude the presence of LA C or D at randomization.

**Subjects untreated with PPI prior to study start will (if possible):**

- (i) start the run-in period with the “investigational week” at visit 1. In such cases an endoscopy with biopsy sampling will be made at visit 1. If insufficient biopsies have been taken at visit 1 then another endoscopy with biopsy sampling will be done at visit 3. In cases of mucosal breaks classified as LA grade C or D at visit 1 or 3 a new endoscopy must be performed at visit 4 prior to randomization. Furthermore, laboratory measurements, 24 hr pH metry, manometry and SAP will be made. If these assessments can be made within 2 weeks from visit 1 then visit 2 and 3 can be left out. The study drug (esomeprazole 40 mg o.d.) will then be dispensed and the subject will continue the run-in period. If the time between first endoscopy (visit 1) and the 24 hour pH metry is more than 2 weeks, the study drug must be dispensed at visit 1 and the subject will follow the same routine as the **treated subject (i)**.

10-year study period

If reflux esophagitis LA grade C or D is found at visit 3, a new endoscopy must be done at visit 4 prior to randomization.

- Subjects will be randomized to either medical treatment or surgery at visit 4. Medical treatment is 20 mg o.d. (start dose) and can be adjusted, but is not to exceed 40 mg daily. Surgery must be performed within 3 months after randomization. The subject is allowed to be treated with esomeprazole 20 mg o.d. and can be adjusted, but is not to exceed 40 mg daily whilst awaiting the surgery. Visit 5 and 6 will only be attended by subjects randomized to surgery.
- Endoscopy with biopsy sampling will be performed at visit 8, 12, 16, 33 and 39. A 24 hour pH metry and SAP will be performed at visit 7 and 16. Endoscopy will be performed at extra visits in case of symptomatic relapse or early discontinuation. A 24 hr pH metry and SAP should be performed in case of dose adjustments (prior to).
- Symptoms will be assessed at each visit except at visit 5 and the telephone visits (visit 30, 32, 34, 36, 38). Laboratory screen will be done at visit 8, 12, 16, 33 and 39 and at early discontinuation visits.
- Patient reported outcomes (PRO) will be assessed by QOLRAD and GSRS at visits 4, 8, 10, 12, 14, 16, 31, 33, 35, 37 and 39 and at early discontinuation visits.
- Body weight will be assessed at visits 4, 8, 12, 16, 33, 39 and at extra visits and at early discontinuation visits.

- All serious adverse events and those adverse events causing premature discontinuation of study drug and/or study will be recorded at each visit except visit 1 and 5 (surgery visit).

During the 10-year study period subjects in both treatment arms having (moderate-severe) recurrent GERD symptoms on at least **3 consecutive days** will be instructed to contact the clinic. The subject will be asked to answer the questions regarding treatment failure and follow the instructions for each treatment arm. In case of dose adjustments, the increased dosage must be taken for 8 weeks before a second dose adjustment is made. A 24 hr pH metry and SAP should be made prior to dose adjustment (only applicable to an adjustment to a higher dose). If the subject is symptom-free and satisfied after this treatment period with an increased dose, a reduction to the previous lower dose should be aimed at. At least one attempt to return to the previous lower dose should be made. After two periods of dose increase due to recurrence of symptoms, the investigator can decide which dose is required to maintain symptoms under control for the remaining study period, but the dose cannot exceed 40 mg o.d. or 20 mg b.i.d.

[figure not shown]
In case of subjects who are satisfied with their treatment, but with temporarily (at least **3 consecutive days**) moderate-severe GERD symptoms, the subject will be offered an endoscopy and:

- Subjects in the medical arm will then receive treatment with esomeprazole 40 mg o.d. for 2-12 weeks according to endoscopic findings and symptomatology. After treatment the subject in the medical arm will continue the study with esomeprazole at a dose which is required to maintain symptoms under control but does not exceed 40 mg daily.
- Subjects in the surgical arm are allowed to have symptomatic treatment (antacids) and will continue the study.

Visits 5 and 6 are only relevant to subjects randomized to surgery.

Interim analyses are planned 3 years (visit 12) and 5 years (visit 16) after last subject randomized (medical arm) or operated (surgical arm) on, to evaluate efficacy and tolerability.

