During the 5-year prolongation, all subjects will visit the hospital after 6, 7, 8, 9 and 10 years for assessments. At 5.5, 6.5, 7.5, 8.5 and 9.5 the subjects will have a telephone visit (hospital visit optional). The hospital visit should be done by the investigator and the telephone should preferably be done the investigator.

Randomized subjects who have discontinued but not withdrawn their informed consent will be followed-up by a phone call from the investigators at 5 and 10 years after randomization. This will also be applicable for subjects who discontinue during the prolonged period. The follow-up phone call consists of questions about the subject's surgery related to GERD, present medical treatment of GERD and present symptom load. For more information see Appendix P to the amendment

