**Table 2 Study plan prolongation**

Visit Nos.	16 a	30 b	31	32 b	33	34 b	35	36 b	37	38 b	39	Extra visit	Discont. Visit h
Year	5 ±6w	5.5 ±6w	6 ±6w	6.6 ±6w	7 ±6w	7.5 ±6w	8 ±6w	8.5 ±6w	9 ±6w	9.5 ±6w	10 ±6w		17
	X												
Endoscopy incl. biopsies Hp status	X				X						X	X f	X
24 hr pH metry, manometry & SAP c												X g	X
QOLRAD, GSRs	X		X		X		X		X		X		X
Symptoms	X		X		X		X		X		X	X	X
Laboratory screen	X				X						X		X
Body weight	X				X						X	X	X
Dispense study drug d	X		X		X		X		X			X	
Compliance d	X		X		X		X		X		X	X	X
Concomitant Medication	X		X		X		X		X		X	X	X
AE e	X	X	X	X	X	X	X	X	X	X	X	X	X
Informed consent and blood sample for genetic research (optional) i	X												

- a Last Visit in the 5-year LOTUS study
- b Telephone Visit (hospital visit optional)
- c If pH monitoring was less than 18 hours, pH metry should be repeated
- d Only for Subjects in the medical arm
- e All SAE and those AE causing premature discontinuation of study drug and/or study
- f In case of administration of healing dose (esomeprazole 40mg o.d)
- g In case of increased dose
- h In case of premature discontinuation
- i See appendix O

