**Need for treatment other than esomeprazole for control of symptoms of reflux disease:**

In order to allow for a stringent assessment of treatment failure ask the following the question:

*“Do you have sufficient control of your heartburn and acid regurgitation?”*

If the answer is **No**, continue with:

*“Do you need other regular drug treatment to control your symptoms?”*

If the answer to this question is **Yes** and the dose of esomeprazole is 20 mg once daily, then the dose is to be increased to 40 mg once daily. The subject will be treated with the increased dosage for 8 weeks before a second dose adjustment can be made.

If the answer to this question is **Yes** and the dose is esomeprazole 40 mg once daily, then the dose is to be changed to 20 mg twice daily. The subject will be treated with the changed dosage for 8 weeks before being classified as a treatment failure if sufficient symptom control has not been achieved.

If the answer to this question is **Yes** and the dose is 20 mg twice daily, then the subject is a **treatment failure and will be withdrawn.**

b/ In the surgical arm:

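### In years 5 to 10 the half-yearly telephone visits leave out symptoms, so the scheduled check for treatment failure drops from every 6 to every 12 months

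*Protocol*

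**What the plan says.** For the prolongation, Protocol 3.1 plans yearly hospital attendance: "all subjects will visit the hospital after 6, 7, 8, 9 and 10 years for assessments". Between these: "At 5.5, 6.5, 7.5, 8.5 and 9.5 the subjects will have a telephone visit (hospital visit optional"). The symptom schedule in the same section then excludes the calls: "Symptoms will be assessed at each visit except at visit 5 and the telephone visits (visit 30, 32, 34, 36, 38").

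In Table 2 the only row marked for visits 30, 32, 34, 36 and 38 is adverse events, and its footnote limits that row: "All SAE and those AE causing premature discontinuation of study drug and/or study". Symptoms and concomitant medication are both unmarked at the calls. In Table 1, by contrast, symptoms are marked every six months from month 6 to month 60.

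There is also an unscheduled route. Section 3.1 reads "During the 10-year study period subjects in both treatment arms having (moderate-severe) recurrent GERD symptoms on at least" three consecutive days are told to contact the clinic, and "The subject will be asked to answer the questions regarding treatment failure and follow the instructions for each treatment arm".

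Under 4.1, a surgical subject who lacks sufficient control and needs other regular drug treatment is a failure at once. A medical subject giving the same answers on 20 mg once daily goes through two dose steps of 8 weeks, and one on 40 mg once daily goes through one: "The subject will be treated with the changed dosage for 8 weeks before being classified as a treatment failure". A medical subject already on 20 mg twice daily fails at once. Under 4.3.2.1, a subject without failure is timed to the last visit.

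**The concern.** The primary endpoint is time to treatment failure, and it depends on someone asking about symptom control and other drug treatment. From year 5 the scheduled occasions for this halve in number, although the site still telephones every subject at the half-year. If a failure is not brought forward by the subject, its date is found later and less exactly, or the subject leaves before it is found. A SAP cannot recover answers that were never collected.

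The adverse-event item does not fill the gap. Section 4.4.2.2 records heartburn, acid regurgitation and dysphagia as adverse events only if they lead to discontinuation or meet a seriousness criterion.

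The end of follow-up raises a second issue. The same answers at visit 39 count at once in the surgical arm, but may have no time to count in the medical arm.

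**Working it through.** **The plan's own figure.** Section 6.1 gives 275 subjects per arm, success of at least 70% at 5 years, and a margin of 8 percentage points with 95% probability.
- Half-width = 1.96 × √(2 × 0.70 × 0.30 / 275) = 7.66 points.
- With continuity correction, adding 1/275, it is 8.02 points.

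The stated 8 is reproduced. It is a 5-year figure, so the schedule after year 5 does not affect it.

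**Delay from scheduled contacts.** For an interval of L months and onset uniform within it, the mean delay is L/2 and the maximum is L.
- Calls without the questions: L = 12, mean 6, maximum 12 months.
- Calls with the questions: L = 6, mean 3, maximum 6 months.

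These are nominal. Table 2 allows ±6 weeks around each visit.

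**Time needed to become a medical-arm failure (4.1).**
- From 20 mg once daily: 8 + 8 = 16 weeks, or 16/52.18 = 0.31 year.
- From 40 mg once daily: 8 weeks, or 0.15 year.
- From 20 mg twice daily: none.

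Lost control first found at year 6, 7, 8 or 9 leaves ample time. Found at the 9.5-year call, the steps end at 9.5 + 0.31 = 9.81 years. Found at visit 39 on either once-daily dose, they cannot be completed.

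**Illustrative number affected.** Assumptions, none of which the documents supply for years 5 to 10:
- a constant hazard taken from 5-year success S5, with h = −ln(S5)/5 and S(t) = exp(−ht);
- no dropout;
- onset of lost control occurs at the failure hazard;
- every medical subject is on 20 mg once daily and would go on to fail.

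The number per 275 with onset between times a and b is 275 × [S(a) − S(b)].

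| 5-year success | h | Onset in last 16 weeks (contact rule works fully) | Onset in years 9 to 10 (nobody calls, schedule as written) | Onset in years 9.5 to 10 (nobody calls, questions added to calls) |
|---|---|---|---|---|
| 70% | 0.0713 | 3.0 | 10.0 | 4.9 |
| 80% | 0.0446 | 2.4 | 8.0 | 4.0 |
| 90% | 0.0211 | 1.4 | 4.7 | 2.4 |

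For 70%: S(9) = 0.526 and S(10) = 0.490, a difference of 3.6 points, and 275 × 0.0362 = 10.0.

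The third column is the same with or without telephone questions, because it comes only from the dose steps meeting the last visit. For subjects already on 40 mg once daily the window is 8 weeks, and that column falls to 0.7 to 1.5.

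**Visit windows.** Visits 38 and 39 are nominally 26 weeks apart. At the extremes of ±6 weeks they are 26 − 12 = 14 weeks apart, which is less than 16. Asking at 9.5 years therefore usually, but not always, leaves room for both steps.

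**The case against.** A reader might infer that failure is looked for only once a year after year 5. The documents do not support that. The contact rule in 3.1 covers the whole 10 years and both arms and leads directly to the failure questions. Table 2 provides an extra visit with symptoms, concomitant medication and dispensing, and any call may be replaced by a hospital visit. The open question about health problems in 4.4.2.2 may also bring out reflux complaints. Moreover, neither schedule table has a row for the two failure questions at any visit. That they are not asked by telephone is inferred from the symptom exclusion and from Table 2; it is not stated.

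This stands, and it narrows the point without removing it. The contact rule relies on the subject to call, and it needs moderate or severe symptoms on three consecutive days. The endpoint needs only insufficient control plus need for other regular drug treatment. Milder loss of control, or symptoms masked by a self-started drug, can miss the trigger. To year 5 the same rule was backed by half-yearly assessment; afterwards that backing halves.

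A reader might also infer that the calls favour the medical arm, or that late medical-arm failures in general cannot be classified. Neither follows. The schedule is the same in both arms. The asymmetry at visit 39 comes from the endpoint's dose steps and the end of follow-up, and it concerns only subjects on a once-daily dose whose lost control is first found in the last 16 or 8 weeks.

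**Conclusion.** The point holds as a modest gap in ascertainment. Scheduled assessment goes from half-yearly to yearly for the second half of the trial, although a half-yearly call takes place. For failures that the contact rule does not catch, the mean delay from scheduled contacts is 6 months instead of 3, assuming uniform onset. Failure times are coarser in both arms, and the 5-year analysis is unaffected.

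The end-of-study asymmetry is separate and small: about 1.4 to 3.0 medical subjects per 275 if the contact rule works fully, and at most about 4.7 to 10.0 if nobody calls. The upper end, 3.6 percentage points, should not be read as the expected bias. It assumes no calls and no dropout, sets 5-year success at the lowest value that 6.1 allows, and applies a failure hazard to loss of control. Telephone questions would reduce the upper range to about 2.4 to 4.9 and would leave the lower one as it is.

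**What to change.** In 3.1 and Table 2, add the two scripted failure questions to telephone visits 30, 32, 34, 36 and 38. Record the date on which control was lost and any regular reflux medication in use. State in 3.1 at which visits the two questions are asked, since neither table shows this. No treatment rule changes. The cost is about a minute in each of five calls already scheduled, and a CRF line.

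Optionally, report the 10-year comparison once more with medical subjects who, at visit 39, lack sufficient control and need other regular drug treatment counted as failures. This should be labelled a bounding sensitivity analysis and not a change to the endpoint, because it would include subjects whom a further dose step might have controlled.

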- 10 Only for subjects with RE LA grade C or D at visits 1 or 3.
- 11 Only body weight
- 12 30 days after visit 5 (surgery)
- 13 Only for subjects in the surgical arm receiving esomeprazole
- 14 Only for subjects in the medical arm
- 15 In case of administration of healing dose (esomeprazole 40 mg o.d.)
- 16 In case of dose adjustment
- 17 In case of premature discontinuation after randomization (visit 4)

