#### 4.4.2.2 Recording of adverse events

SAEs and AEs causing premature discontinuation of study drug and/or study will be recorded retrospectively by the investigator in the Case Report Form at visit 2 and the following visits. If any SAE or AE causing premature discontinuation of study drug and/or study are ongoing at the subjects last visit in the study, they must be followed up after 2 to 4 weeks and thereafter as long as medically indicated. This can be done either as an extra visit to the clinic or by written or verbal contact with the subject.

Spontaneously reported SAEs and AEs causing premature discontinuation of study drug and/or study, objective findings and observations, and SAE and AEs causing premature discontinuation of study drug and/or study reported in response to the standardized question “Have you had any health problems since the previous visit?” will be recorded in the CRF. Start and stop date (or marked as ongoing), outcome, maximum intensity, seriousness, and action taken with regard to investigational product and if the AE caused subject to discontinue the study will be recorded. Maximum intensity will be rated according to the following scale:

- |              |  |
|--------------|--|
| 1 = Mild     | - awareness of sign or symptom, but easily tolerated                 |
| 2 = Moderate | - discomfort sufficient to cause interference with normal activities |
| 3 = Severe   | - incapacitating, with inability to perform normal activities        |

It is important to distinguish between serious and severe AEs. Severity is a measure of intensity whereas seriousness is defined by the criteria in Section 4.4.2.1. An AE of severe intensity need not necessarily be considered serious. For example, nausea, which persists for several hours, may be considered severe nausea, but not a SAE. On the other hand, a stroke which results in only a limited degree of disability may be considered a mild stroke but would be a SAE.

Abnormal test results from laboratory investigations or endoscopy investigations (including biopsies) that meet any criteria of an SAE must be reported in accordance with the SAE reporting procedures (see Section 4.4.2.3).

Symptoms included in the efficacy variables

- Section 4.3.5.1 GERD symptoms (i.e. heartburn, acid regurgitation, dysphagia)
- Section 4.3.5.1. other GI symptoms (i.e. epigastric pain, flatulence, bloating, ability to vomit, ability to belch, diarrhoea)

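### Adverse events are not recorded at the surgery visit and the next visit's question looks back only to it, so in the surgical arm no scheduled question covers the wait for surgery

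*Protocol*

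**What the plan says.** Four parts of the Protocol bear on this.

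- **Which visits record events.** Section 3.1 (10-year study period) says that SAEs and adverse events leading to discontinuation "will be recorded at each visit except visit 1 and 5 (surgery visit"). Table 1 agrees: its adverse-event row is marked at visits 2, 3, 4 and 6 onwards, and is empty at visit 5. Section 4.4.2.2 says that the same events are "recorded retrospectively by the investigator in the Case Report Form at visit 2 and the following visits", with no exception for visit 5.
- **What is asked.** Section 4.4.2.2 gives one standardized question: "Have you had any health problems since the previous visit"? The same sentence also admits other sources, beginning with "Spontaneously reported SAEs and AEs causing premature discontinuation of study drug and/or study, objective findings and observations".
- **Who attends.** Section 3.1: "Visit 5 and 6 will only be attended by subjects randomized to surgery".
- **Timing.** Section 3.1: "Surgery must be performed within 3 months after randomization". A Table 1 footnote places visit 6 "30 days after visit 5 (surgery").

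**The concern.** The look-back of the standardized question is tied to the preceding visit. That works only if events were asked about at that visit. At visit 5 they are not, so the chain of look-back periods breaks between visit 4 and visit 5, and only for subjects randomized to surgery. SAEs and discontinuations due to adverse events are the main clinical safety data of an open comparison. They feed the interim evaluations of tolerability (Section 6.2.4) and the six-monthly SAE review by the Steering committee (Section 6.3). Solicited safety data should cover the same time in both arms. Separately, sites have two statements about visit 5 that they cannot both follow as written.

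**Working it through.** The Protocol states no figure on this point. The check is a reconciliation of the schedule, followed by the size of the uncovered interval.

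**Step 1: follow the question through each arm.**

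| Arm | Visit | Timing | Events recorded? (Section 3.1, Table 1) | Period the question covers |
|---|---|---|---|---|
| Surgical | 4 | month 0 | yes | since the previous run-in visit |
| Surgical | 5 | within 3 months | no | none |
| Surgical | 6 | 30 days after visit 5 | yes | visit 5 to visit 6 |
| Surgical | 7 | month 6 | yes | visit 6 to visit 7 |
| Medical | 4 | month 0 | yes | since the previous run-in visit |
| Medical | 7 | month 6 | yes | visit 4 to visit 7 |

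The surgical arm has no scheduled look-back for visit 4 to visit 5. The medical arm has no such interval.

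**Step 2: subtract what other routes catch.**

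- Operation and recovery: Section 4.3.6.1 has a standardized CRF record of per-operative complications. Section 4.3.7.1 has the investigator assess the early post-operative course at visit 6. Under Section 4.4.2.2, any such sign or symptom that meets an SAE criterion must be reported as an SAE.
- Leaving the study during the wait: Section 3.3.5.4 and the discontinuation column of Table 1 record SAEs and discontinuation events.
- Any SAE the investigator learns of: Section 4.4.2.3 requires a report within one day, whatever the visit.

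Two kinds of event during the wait remain: (i) an SAE that does not end participation and does not otherwise reach the investigator, such as an admission elsewhere that the subject does not volunteer; and (ii) an adverse event that stops the pre-operative study drug while the subject stays in the study and goes on to surgery. The second kind is within the recording rule, which covers stopping the drug as well as stopping the study.

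**Step 3: size of the interval.** Inputs: 275 subjects per arm (Section 6.1) and a wait of at most 3 months (Section 3.1). The Protocol gives no expected wait, so 1 and 2 months are assumptions.

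Subject-years uncovered = 275 × wait in months / 12.

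- 1 month: 275 × 1/12 = 22.9
- 2 months: 275 × 2/12 = 45.8
- 3 months (maximum): 275 × 3/12 = 68.75, about 69

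As a share of follow-up, the maximum is 3/120 months = 2.5% of ten years, or 3/6 = 50% of the first six months. In the medical arm it is 0. These are amounts of time, not counts of missed events. They are upper bounds, because they take all 275 subjects as operated on, and Section 6.2.1 foresees that some will refuse.

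**The case against.** The case against rests on four arguments.

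1. **The gap depends on a literal reading.** The previous visit could be taken to mean the last visit at which events were recorded, which before visit 6 is visit 4. Events are recorded retrospectively with start dates, and the CRF and Appendix L, which might settle the look-back, are not shown. This stands as a caution. The Protocol text does not define the term, however, and visit 5 is an ordinary numbered visit at which Table 1 marks drug dispensing and compliance.
2. **The investigator will usually know.** Visit 5 is a visit with the investigator, and spontaneous reports and one-day SAE reporting apply throughout. This stands and makes the loss small. It does not close the gap, because those routes depend on the subject volunteering the event or the investigator already being aware of it.
3. **The contradiction is slight.** Section 4.4.2.2 may only be saying when recording starts. That is possible, but its wording, "in the Case Report Form at visit 2 and the following visits", takes in visit 5.
4. **Safety is only descriptive.** Table 4 plans no formal comparison. This is correct, and it limits the consequence.

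A reader might go further and infer that the operation day is never asked about. The documents do not support that: the per-operative record and the visit 6 post-operative assessment cover it. A reader might also infer that the safety comparison is biased in favour of surgery. That is not shown either. The uncovered time is a wait during which esomeprazole is allowed (Section 3.1), so an event missed there is not a missed surgical event. The surgical arm also has an extra adverse-event visit (visit 6) and structured operative records that the medical arm lacks, so the net direction of any difference in ascertainment is uncertain.

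**Conclusion.** The point holds in a narrow form. Section 3.1 and Table 1 exclude visit 5 from adverse-event recording, and Section 4.4.2.2 does not. Under the literal look-back, no scheduled question covers the wait from visit 4 to visit 5 in the surgical arm alone. The uncovered time is at most 3 months per subject, about 69 subject-years in all, or 2.5% of ten years. What can be lost is limited to the two kinds of event identified in the working. The effect on the descriptive safety comparison is likely small, and its direction cannot be stated from the documents. The conclusion assumes that the question is put as worded and that the CRF does not already extend its look-back. It is worth correcting because the gap is in one arm only, the texts conflict, and the correction is nearly free.

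**What to change.** Reconcile Section 3.1, Table 1 and Section 4.4.2.2 by one of two routes. Either is enough; doing both would ask about the wait twice.

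- **(a) Record at visit 5.** Mark the adverse-event row of Table 1 at visit 5, and change Section 3.1 so that only visit 1 is excepted. The bracketed surgery label must go as well; otherwise it would attach to visit 1.
- **(b) Keep the exclusion.** State it in Section 4.4.2.2, and word the visit 6 question to ask about health problems since adverse events were last recorded (visit 4).

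The cost is one extra CRF line under (a) or a reworded question under (b), at a visit that already takes place, plus the matching text edits. No treatment, endpoint or analysis changes.
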